1.1. BACKGROUND AND RATIONALE

Hepatitis B virus (HBV) is a viral illness that results in inflammation of the liver. It causes significant morbidity and mortality worldwide and is the most common chronic viral infection in the world. It is estimated that up to 30% of the world's population has serological evidence of a current or past HBV infection. HBV can manifest either as an acute illness causing nausea, malaise, abdominal pain and jaundice or as an often asymptomatic chronic infection. Chronic HBV infection can lead to liver cirrhosis and hepatocellular carcinoma.

HBV is blood borne and transmitted via exposure to infected blood or bodily fluids contaminated by blood. One of the most common forms of transmission is vertical or perinatal transmission of HBV from infected mothers to neonates. Low and middle-income countries have disproportionally higher rates of HBV thus there is a high prevalence in immigrants to higher-income countries. Of those who develop an acute HBV infection, 95% of babies, 20-30% of children and less than 5% of adults will go on to have a chronic infection. There is no available treatment for an acute HBV infection whilst antivirals such as Tenofovir can improve chronic HBV infections by slowing cirrhosis and reducing the risk of liver cancer.

Given the complications associated with HBV, prevention of transmission is the best method for controlling this infection. Prevention includes avoidance of transmission from infected people via counselling against high risk behaviours, screening of blood products and more stringent infection control in healthcare settings through universal precautions. By far the most effective way of controlling HBV is through vaccination.

The first HBV vaccine was developed in 1982 and is in widespread use. Most vaccines for HBV were developed using recombinant DNA to express a protein (antigen) against hepatitis (HBsAg). HBV vaccines are available in monovalent (single), combination (with Hepatitis A) and multivalent forms (with multiple other vaccines). Routine immunisation of neonates is a common practice worldwide with the WHO recommending a dose of HBV at birth followed by either a 2 or 3 dose schedule. Completion of either of these programmes induces protective antibody levels in up to 95% of infants, children and adolescents.

The burden of HBV in the UK reflects that of other high-income countries. In 2016 there were 453 cases of acute HBV reported and an annual incidence of 0.82 per 100,000 people. During the same period 11,901 cases of HBV were recorded, the remainder being chronic infections. The UK added a vaccine for HBV to the routine childhood immunisation schedule in 2017 as part of a multivalent vaccine. Multivalent vaccines are cost effective on a population level. They reduce the number of needles that need to be administered thus reducing the risk of complications, they minimise the number of vaccine healthcare visits needed and associated costs and they improve compliance and vaccine coverage.

Characteristics of licensed vaccines

1.2. 6 in 1(IH) (Infanrix hexa)

Developed by GlaxoSmithKline, 6 in 1(IH) is a multivalent vaccine that protects against diphtheria, tetanus, pertussis, poliomyelitis, *Haemophilus influenza* type B (Hib) and hepatitis B virus (HBV). It is licensed in Europe and has been widely used internationally with data to support its efficacy and safety. It is available in a powder and suspension for injection form. 6 in 1(IH) has been included in the UK's routine immunisation schedule at 2, 3 and 4 months of age since 2017. It is made up of diphtheria and tetanus toxoid, Bordetella pertussis antigens (pertussis toxoid, filamentous haemagglutinin and pertactin), inactivated poliovirus (type 1 - 3), Hib polysaccharide conjugated to tetanus toxoid as the carrier protein and hepatitis B surface antigen.

1.1.3. 6 in 1(V) (Vaxelis)

One of the other multivalent vaccines that contains Hepatitis B currently licensed in Europe is 6 in 1(V). Developed jointly by Merck/MSD and Sanofi Pasteur, 6 in 1(V) is available as a fully liquid and ready to use injection and protects against the same organisms as 6 in 1(IH) however the structure of some components differs. 6 in 1(V) contains diphtheria and tetanus toxoid, *Bordetella pertussis* antigens (including pertussis toxoid, filamentous haemagglutinin, pertactin and fimbriae types 2 and 3), inactivated poliovirus (including type 1 - 3), Hib polysaccharide conjugated to a meningococcal outer membrane complex (OMPC) and hepatitis B surface antigen. It is the structure of the Hib component that may be relevant to the use of 6 in 1(V) in the UK. 4CMenB is the meningococcal B vaccine currently in use in the UK's routine

immunisation schedule at 2, 4 and 12 months of age. The structure of 4CMenB includes meningococcal outer membrane vesicles which carries with it a theoretical risk of a carrier induced epitopic suppression of the Hib responses of 6 in 1(V) when given concurrently with 4CMenB. This interaction has the potential to lead to the creation of a birth cohort with sub-optimal responses to the Hib antigen of 6 in 1(V) and thus risk a re-emergence of Hib as was seen in the UK in 1999 – 2003.

There is also the possibility that the combination of the OMPC from 6 in 1(V) and 4CMenB could cause increased systemic and local vaccine adverse reactions when co-administered (as compared to adverse reactions that can occur using the existing schedule). In the absence of any evidence to show that these concerns are unfounded, it is possible that the use of 6 in 1(V) in the UK immunisation schedule would be seen as inappropriate. This could limit the flexibility of vaccine procurement for the UK government.

We are conducting a head-to-head unblinded open randomised trial comparing the immunogenicity and reactogenicity at 5 and 13 months of both licensed DTaP-Hib-IPV-HepB vaccines when administered at 2, 3 and 4 months of age alongside the current UK vaccination schedule (including 4CMenB).

Section 2. Study Methods

2.1 Trial Design

This study is an open label, non-inferiority 1:1 randomised clinical trial conducted by the UKPVG sites led by the Oxford Vaccine Group (OVG). The study initially intended to enrol 240 healthy infants residing in the UK aged between 8 and 13 weeks. There are 6 visits in total throughout this study including two blood tests. These visits take place in participant's homes or a suitable, convenient location. Participants will be involved in the study for approximately 11 months (from enrolment at 8 weeks minimum to the last blood test at 13 months of age).

2.2 Sample size

The initial sample calculation was based on the following assumptions:

1. The non-inferiority margin is 0.5 fold-difference between the GMC in the 6 in 1(V)arm and that in the 6 in 1(IH) arm (reference) or -0.3 absolute difference of GMC on log scale (base 10).

2. The standard deviation of GMC on log scale (base 10) is 0.72

3. The true difference of GMC on log scale (base 10) is 0.

Based on the above assumptions, the intent was to recruit 104 infants for each arm to achieve 85% of power at two-sided 5% significance level. The attrition rate was expected to be approximately 10%. To incorporate further allowances for protocol violations and unexpected dropouts, the initial target sample size was 240 infants (120 per arm).

The protective threshold for Hib is 0.15 μ g/ml. (13) Assuming the proportion of infant with anti-PRP IgG concentrations at 5 months of age \geq 0.15 µg/ml is 91%, this trial would have had >70% of power with two-sided 5% significance level to claim the 6 in 1(V) is non-inferior to 6 in 1(IH) at a margin of 10%.

After reviewing the disruption on clinical activities by COVID-19 from March 2020 onwards, and the urgency to obtain the data for policy making in the UK, the study team decided to evaluate the study power based on the recruitment up to the time this was paused for the COVID-19 Statistical Analysis Plan, Version 2.0

pandemic, and decided to increase the type I error from two-sided 5% (one-sided 2.5%) to onesided 5%, which is a common type I error rate in non-inferiority trials. At this stage the study had recruited 194 participants. From these there was approximately 172 participants with blood samples likely to be available for primary endpoints in the ITT analysis. Based on the original assumptions and the 5% type I error, the current study power is 85%. Since the current study recruitment has achieved the planned power based on the adjusted type I error, the study CI, sponsor and funder group decided not to resume recruiting and continue with a sample size of 194 participants.

2.4 Objectives and outcome measures

Primary and secondary objectives are reported in Table 1, alongside the outcome measures and timepoint of evaluation for each measure.

Objectives	Outcome Measures	Timepoint(s) of evaluation of this outcome measure (if applicable)
Primary Objective Compare the immunogenicity of the Hib component of 6 in 1(IH) and 6 in 1(V) when co-administered with 4CMenB in the UK routine immunisation schedule at 5 months of age.	Measurement of anti-PRP (Hib) IgG concentrations at 5 months of age as measured by ELISA.	At 5 months of age (at least 4 weeks after administration of the last dose of either 6 in 1(IH) and 6 in 1(V) primary immunisations).

Table 1 – Objectives, outcome measures, and timepoints

Secondary Objectives Compare the anti-PRP (Hib) IgG concentrations at 13 months of age (1 month after administration of Hib-MenC at 12 months of age) in participants primed with 6 in 1(IH) and 6 in 1(V).	Assess the anti-PRP (Hib) IgG concentrations at 13 months of age as measured by ELISA.	At 13 months of age (at least 4 weeks after the Hib- MenC vaccination at 12 months of age).
The immunogenicity of the other antigens in the routine immunisation schedule incorporating either 6 in 1(IH) or 6 in 1(V).	Assess the IgG concentrations at 5 and 13 months of: a.Diphtheria-toxoid b.Tetanus toxoid c.Hepatitis B virus d.Vaccine-serotype pneumococcal capsule antigens e.Pertussis antigens f.Poliovirus neutralising antibodies Assess serum bactericidal titres at 5 and 13 months of age of: a. 3 reference serogroup B meningococcal strains b. Serogroup C meningococcus	At 5 and 13 months of age (approximately 4 weeks after completion of the primary routine immunisations and approximately 4 weeks after the booster doses in the routine immunisation schedule).
The reactogenicity of 6 in 1(IH) and 6 in 1(V) when administered in the routine UK immunisation schedule.	Solicited local and systemic adverse events within 5 days of immunisations	In the 5 days post immunisation in participant diaries

Section 3. Analysis – general considerations

The primary analysis will be conducted on the modified intent-to-treat basis, i.e. anyone who received at least one dose of study vaccine with the study endpoint available will be included in this analysis. The per-protocol analysis will be considered as a sensitivity analysis to rule out the effect of non-compliance. The non-compliance is defined as a visit outside the pre-specified window or missing doses of vaccination (Table 2). Windows of inclusion will be relaxed to allow +/-7 days difference to the visit schedule for visits 1, 2, 3, 4, and 6, and +/-14 days difference to the visit schedule for visits 1, 2, 3, 4, and 6, and +/-14 days difference to the visit schedule for visits 1, 2, 3, 4, and 6, and +/-14 days difference to the visit schedule for visits 1, 2, 3, 4, and 6, and +/-14 days difference to the visit schedule for visits 1, 2, 3, 4, and 6, and +/-14 days difference to the visit schedule for visits 1, 2, 3, 4, and 6, and +/-14 days difference to the visit schedule for visits 1, 2, 3, 4, and 6, and +/-14 days difference to the visit schedule for visits 1, 2, 3, 4, and 6, and +/-14 days difference to the visit schedule for visits 1, 2, 3, 4, and 6, and +/-14 days difference to the visit schedule for visit schedule f

Group	Visit 1	Visit 2	Visit 3	Visit 4	Visit 5	Visit 6
Age of participant	2 months	3 months	4 months	5 months	12 months	13 months
Visit windows	8 – 13 weeks of age	28-42 days after visit 1	28-42 days after visit 2	28-42 days after visit 3	12 months of age (+28 days)	28-42 days after visit 5
Relaxed window	N/A	21-49 days after visit 1	21-49 days after visit 2	21-49 days after visit 3	350-406 days of age	21-49 days after visit 5
Visit description	Enrolment Vaccination	Vaccination	Vaccination	Blood sampling	Vaccination	Blood sampling

Table 2 – Trial visit schedules

The analysis on primary outcome of the 5-month anti-PRP Hib IgG concentrations and secondary outcomes of safety and other 5-month antigens will be conducted once the 5-month data are available for all participants, while the trial will continue to follow up all participants

until 13 months of age. The final analysis for the other outcomes will be carried out once the 13-month data are available for all participants.

The concentration of IgG is expected to be positively skewed and thus mathematical transformations (log10) will be applied, where appropriate, in order to render a normal distribution. Values below the lower limit detectable by the assay will be imputed a value half the lower limit of detection prior to log transformation. Distributional assumptions will be assessed graphically and if these assumptions are violated alternative analysis methods (e.g. non-parametric) or alternative transformations will be used. For assays that have an upper limit of detection, the value of the upper limit will be used, and the data will be transferred to categorical data for analysis.

Continuous variables that follow an approximately normal distribution will be summarised using means and standard deviations. Skewed continuous variables will be summarised using medians and inter-quartile ranges if there is no appropriate transformation to render a normal distribution. Categorical variables will be summarised using frequencies and percentages.

Baseline characteristics will be summarised for each group to describe the study population. No formal statistical comparisons of baseline characteristics between randomised groups will be conducted. Patient throughput from census, enrolment, through randomisation, follow up and analysis will be presented in a CONSORT flow diagram. This will contain the numbers of participants randomly assigned to each group, receiving different doses of study vaccine, completing the study and analysed for the primary outcome. It will also include a breakdown of reasons for withdrawal.

A P value lower than 0.05 (one-sided) will be considered to be significant for the non-inferiority analysis of the primary objective. For superiority tests, a 2-sided P value less than 0.05 will be considered significant.

Section 4. Analysis

4.1 Outcome Definitions and Analysis Methods

4.1.1 Primary Endpoint

The primary outcome is anti-PRP Hib IgG concentrations at 5 months of age as measured by ELISA. The geometric mean concentrations (GMC) of anti-PRP IgG will be compared between 6 in 1(IH) and 6 in 1(V) under the hypothesis:

Ho: $GMC_{6 \text{ in } 1(V)} / GMC_{6 \text{ in } 1-(IH)} \le 0.5 \text{ or } log_{10} GMC_{6 \text{ in } 1(V)} - log_{10} GMC_{6 \text{ in } 1(IH)} \le -0.3;$

H₁: GMC₆ in 1(V) / GMC₆ in 1(IH) > 0.5 or log_{10} GMC₆ in 1(V) - log_{10} GMC₆ in 1(IH) > -0.3.

The GMC will be transferred using logarithmic transformations (base 10) to render a normal distribution.

We will test the above hypothesis using Student's t-test on log_{10} GMC. The mean difference of log_{10} GMC will be presented with the one-sided 95% confidence interval (CI). The difference will be calculated as the mean of log_{10} GMC in 6 in 1(V) arm compared to that in the 6 in 1(IH) arm. We will claim 6 in 1(V) is non-inferior to 6 in 1(IH) if the lower CI of log_{10} GMC difference lies above -0.3. If a non-inferiority of 6 in 1(V) to 6 in 1(IH) is claimed, the Student's t-test will also be used to test superiority and two-sided 95% CI will be presented. If the data cannot be rendered normal after a log transformation, Wilcoxon rank sum tests will be used in place of the Student's t-test.

The proportion of infant with anti-PRP Hib IgG concentrations at 5 months of age \geq 0.15 µg/ml will be calculated with the corresponding 95% Yates's continuity-corrected CIs for 6 in 1(IH) and 6 in 1(V) arms. Although the study is not powered based on the proportion of protection, the difference between the two arms will be reported with one-sided 95% Yates's continuity-corrected CIs, and the non-inferiority margin for proportion of protection is -10%. Fisher's Exact tests will be performed and reported with one-sided 95% confidence intervals where expected values are low.

The definitions of the analysis population can be found in section 3 for both primary and sensitivity analyses. Further sensitivity analyses will be carried out using multiple regression to adjust for potential covariates, including gender, age in days at first dose, and maternal pertussis immunisation history (Y/N).

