Appendix A: Amendment history

Amendment No.	SAP Version No.	Date issued	Author(s) of changes	Details of Changes made
1	2.0	02.07.21	[name]	Additional of details of relaxed windows around visit schedules; addition of non-parametric tests for non-normal data; correlates of protection details for the study antigens; table formatting.

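### The Wilcoxon fallback for the primary endpoint does not test the 0.5-fold margin, so the stated non-inferiority rule cannot be applied to it

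*SAP*

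**What the plan says.** SAP 2.2 sets the margin: "The non-inferiority margin is 0.5 fold-difference between the GMC in the 6 in 1(V)arm" and the reference arm, equivalently -0.3 on the log10 scale. SAP 4.1.1 states the null as a GMC ratio of 0.5 or less and tests it by Student's t-test on log10 values. Non-inferiority is claimed if the lower limit of the one-sided 95% interval for the mean log10 difference lies above -0.3. A superiority t-test follows if that succeeds.

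The same paragraph ends with the fallback: "If the data cannot be rendered normal after a log transformation, Wilcoxon rank sum tests will be used in place of the" Student's t-test. It gives no shift, estimate, interval or replacement decision rule.

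Section 3 has a general provision, triggered by a graphical check without a stated criterion, that "alternative analysis methods (e.g. non-parametric) or alternative transformations will be used". The amendment history lists the "addition of non-parametric tests for non-normal data" among the changes in version 2.0.

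**The concern.** The primary claim is about a ratio of geometric means against a fixed margin, and the decision rule needs a confidence limit for that ratio. A standard rank sum test has equal distributions as its null and returns a p-value, with no limit to set against -0.3. If the plots are judged non-normal, the plan would replace a test of the margin with a test that does not mention it. The single primary decision would then depend on whoever fills the gap at the time of analysis.

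**Working it through.** **Inputs.** Margin 0.3 log10 (SAP 2.2); SD: "The standard deviation of GMC on log scale (base 10) is 0.72"; true difference: "The true difference of GMC on log scale (base 10) is 0". Sample after the pause: "approximately 172 participants with blood samples likely to be available for primary endpoints in the ITT analysis". One-sided 5% error (SAP 2.2 and Section 3). The 86/86 split is assumed from 1:1 allocation (172/2 = 86).

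**Reproducing the plan's figures.** The plan says "the intent was to recruit 104 infants for each arm to achieve 85% of power at two-sided 5% significance level".
- n per arm = 2 × 0.72² × (1.960 + 1.036)² / 0.3² = 103.4, so 104. This agrees.
- At 86 per arm, SE = 0.72 × √(2/86) = 0.1098 and 0.3/0.1098 = 2.732. Power = Φ(2.732 − 1.645) = 86.2%, or 85.9% by the noncentral t. The SAP's 85% agrees to within about 1 point.

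**Simulating the fallback.** 10,000 trials per row, 86 per arm. Entries are the percentage of trials with one-sided p < 0.05 in favour of 6 in 1(V). A true difference of 0 shows power for non-inferiority. A true difference of -0.3 shows false claims, nominally 5%.

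| Assumed log10 data | True difference | Wilcoxon as written | Wilcoxon, 0.3 added to V | t-test, 0.3 added to V |
|---|---|---|---|---|
| Normal, SD 0.72 | 0 | 4.9 | 83.9 | 85.6 |
| Normal, SD 0.72 | -0.3 | 0.0 | 5.1 | 5.2 |
| Right-skewed (exponential), same shape | 0 | 4.9 | 98.9 | 86.6 |
| Right-skewed (exponential), same shape | -0.3 | 0.0 | 5.0 | 5.0 |
| Left-skewed, same shape | 0 | 5.2 | 98.9 | 85.6 |
| Left-skewed, same shape | -0.3 | 0.0 | 5.4 | 5.0 |
| Unequal: IH normal, V with 20% low responders | 0 | 10.3 | 91.2 | 85.3 |
| Unequal: IH normal, V with 20% low responders | -0.3 | 0.0 | 10.4 | 5.2 |

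The simulation standard error near 5% is √(0.05 × 0.95/10,000) = 0.2 points.

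**The unequal case.** Before the shift, V is 80% centred at 0.26 and 20% at -1.04, each with SD 0.5. The mean is 0.8 × 0.26 − 0.2 × 1.04 = 0, and the SD is √(0.25 + 0.8 × 0.26² + 0.2 × 1.04²) = 0.72. With the mean lowered by exactly 0.3, the main group of V sits at 0.26 − 0.30 = -0.04, almost level with IH. The low responders carry most of the loss in GMC. Ranks register that these infants are low but not how low, so the shifted test too often finds V acceptable. A further assumed unequal-shape case gave about 15% for the shifted Wilcoxon and 5% for the t-test.

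**Reading the table.**
1. As written, the Wilcoxon test succeeds in about 5% of trials with equal distributions. That is simply its own size, so it is a superiority test.
2. Tied to the margin, it works well when the shapes match and fails to hold its error rate when they do not.
3. The t-test stays at 5.0% to 5.2% error in every shape tabulated, so non-normality at this sample size does not call for a fallback.

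**The case against.** **The sentence has milder readings.** A test used in place of the t-test could be meant to test the same hypothesis, that is, with the margin shift. Or the sentence, which directly follows the superiority test, could concern superiority only. Or the claim rule, which is attached to the interval, could survive because only the test is replaced. Each reading is possible, but the SAP states none of them. The first holds its error rate only with equal shapes. The second leaves non-inferiority with the unspecified methods of Section 3. The third allows a Wilcoxon p-value and a t-interval to disagree, with no rule for which decides.

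**The fallback may never be used.** Section 3 expects the log transformation to work, and nothing in the document shows that it will not. This stands: the problem is conditional. Setting values below the detection limit to half that limit could create a spike at the floor, but how many values would be affected is unknown.

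**A reader might infer that the fallback lets a non-significant difference pass as non-inferiority.** With normal data at a true difference of -0.3, that would give false claims in 15.7% (one-sided) to 24.6% (two-sided) of trials. The SAP does not support this reading. Section 3 requires a one-sided p below 0.05 for non-inferiority, and 4.1.1 requires the lower limit to exceed -0.3. Nor is the direction general: with same-shape skewed data the figures were 1.1% to 2.5%.

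**A reader might also infer a data-driven change,** because the trial is open label and the non-parametric tests came in with version 2.0. The SAP does not say whether 5-month data had been seen, so nothing rests on this. Likewise, the alternative transformations appear only in the general section; 4.1.1 goes from log10 directly to Wilcoxon.

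**Conclusion.** The point holds, conditionally on the fallback being triggered. The rule in 4.1.1 then replaces a test of the GMC ratio against 0.5 with one that does not test it, and leaves the claim rule with no limit to use. Taken literally, the chance of a non-inferiority claim with equal arms falls from about 85% to about 5%. That literal use does not inflate false claims in the cases simulated; the harm is loss of power and an undefined decision. Under the margin-shifted reading, error at the margin is about 5% with equal shapes and about 10% to 15% in assumed unequal-shape cases, where the t-test holds about 5%.

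These figures rest on an assumed 86/86 split and the SAP's SD of 0.72. The 5% against 85% comparison uses normal data, which would not itself trigger the fallback, although the same-shape skewed rows give much the same result. The non-normal shapes are assumptions; the SAP gives none. An arm with more low responders is plausible, given the SAP's stated concern about suppressed Hib responses with 6 in 1(V), but it is not established.

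**What to change.** In SAP 4.1.1:
- State that the t-based one-sided 95% interval for the mean log10 difference (Student or Welch) is the only non-inferiority decision rule, whatever the distribution looks like.
- State that the alternative methods and transformations of Section 3 do not apply to that decision.
- Limit the Wilcoxon test to the superiority comparison, or to a supportive analysis reporting a Hodges-Lehmann shift with its one-sided 95% lower limit against -0.3, with the equal-shape assumption noted.
- Optionally, add a bootstrap interval for the GMC ratio as a sensitivity analysis.

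The cost is a few sentences in the SAP and a few lines of code. No new data and no change to the sample size are needed.

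### Hib seroprotection (SAP 4.1.1): Fisher's exact test does not address the -10 point margin, and the Yates-corrected interval is needlessly conservative

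*SAP*

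**What the plan says.** SAP 4.1.1 adds to the primary GMC comparison a comparison of the proportions at or above 0.15 µg/ml at 5 months. The arm difference gets a one-sided 95% Yates interval, with a formal margin: "continuity-corrected CIs, and the non-inferiority margin for proportion of protection is -10" percent. The section also says that the study is not powered on this proportion. The next sentence provides for sparse data: Fisher's "Exact tests will be performed and reported with one-sided 95% confidence intervals where expected values are low". It gives no threshold for low, no parameter for the interval and no link to the margin.

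SAP 2.2 assumes that the proportion protected "is 91%, this trial would have had >70% of power with two-sided 5% significance level" for a 10% margin. It names no sample size and no method for that figure. The same section then reports that the team "decided to increase the type I error from two-sided 5% (one-sided 2.5%) to onesided 5" percent and stopped at 194 recruits, about 172 of them likely to have primary-endpoint samples. Power is restated for the GMC (85%) but not for seroprotection.

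**The concern.** A non-inferiority margin on a difference in proportions needs an interval or test on that scale. Fisher's exact test has equal proportions (odds ratio 1) as its null, and the interval usually paired with it is for the odds ratio. Neither can be set against -10 points. A significant Fisher result is not needed for non-inferiority, and a non-significant one does not show it.

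Separately, the continuity correction lowers the limit by (1/n1 + 1/n2)/2, about 1.2 points at 86 per arm. A vaccine with truly equal seroprotection then fails the margin more often than under an interval that already holds its nominal error rate.

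The trial was motivated by possible suppression of Hib responses, and this is the analysis that speaks most directly to protection. Its rule should be unambiguous before the data are analysed.

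**Working it through.** **Inputs.** From SAP 2.2: 91% protected (taken as equal in both arms), margin 10 points, originally two-sided 5% and now one-sided 5%; 104 evaluable per arm, 120 per arm recruited, about 172 finally evaluable. From 2.1: allocation 1:1. Assumed: 86 per arm (172/2), and an expected count below 5 as the meaning of low.

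**1. The plan's own figure.** Without continuity correction, power = Φ(0.10/SE − z), SE = √(2 × 0.91 × 0.09/n).
- n = 104, z = 1.96: SE = 0.0397; Φ(0.10/0.0397 − 1.96) = 71.2% (full binomial enumeration 72.5%).
- n = 120, z = 1.96: 77.2%.

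A figure above 70% is therefore reproduced by the uncorrected formula at either size.

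**2. The same design with the planned Yates interval.** The correction is (1/n + 1/n)/2 = 1/n, so power = Φ((0.10 − 1/n)/SE − z).
- n = 104: Φ((0.10 − 0.0096)/0.0397 − 1.96) = 62.5% (enumeration 63.1%).
- n = 120: 69.9% (enumeration 70.2%).

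By enumeration at 104 per arm, Miettinen-Nurminen gives 67.0% and Newcombe 67.1%.

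**3. The final design: 86 per arm, one-sided 5%.** Power is at 91% in both arms. Type I error is at 81% v 91%, exactly on the margin. All values are by full enumeration of the two binomials.

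| Interval | Power | Type I error |
|---|---|---|
| Yates-corrected | 66.2% | 3.5% |
| Miettinen-Nurminen | 70.6% | 5.0% |
| Newcombe | 72.5% | 5.2% |
| Uncorrected Wald | 74.9% | 5.6% |

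The formula for Yates gives 64.8%. Yates would need 97 per arm to reach 70% at one-sided 5%.

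**4. When Fisher would apply.** At 91%, the expected unprotected count is 86 × 0.09 = 7.7 per arm. It falls below 5 when pooled protection exceeds 1 − 5/86 = 94.2%, about 3 points above the assumed rate.

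**5. What Fisher says about the margin.** Two tables at 86 per arm, both with expected unprotected counts below 5:
- 79/86 (6 in 1(V)) v 84/86 (6 in 1(IH)): expected (7 + 2)/2 = 4.5 unprotected per arm; difference −5/86 = −5.8 points. Two-sided Fisher p = 0.17. One-sided 95% lower limits: −11.4 (uncorrected), −12.5 (Yates), −12.2 (Newcombe). Non-inferiority is not shown, yet Fisher finds no difference.
- 83/86 v 83/86: expected 3 per arm. One-sided Fisher p = 0.66. Lower limits: −5.8 (Yates), −5.3 (Newcombe). Non-inferiority is shown, yet the Fisher p-value cannot say so.

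**The case against.** Several stronger readings are tempting, and the document does not support them.

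- **That the stated power is wrong.** A reader might infer that a figure above 70% is unattainable with Yates. But 2.2 gives neither n nor method, and it phrases the figure as what the original trial would have had. Yates reaches 70.2% if all 120 per arm are evaluable. That match is marginal and leaves nothing for the attrition of about 10% that 2.2 itself expects, but it rules out calling the figure an error.
- **That Yates costs the whole drop from 71% to 63% at 104 per arm.** The 71% comes from an uncorrected Wald interval, which is slightly anti-conservative (5.6% at 86 per arm, nominal 5%). Against a score interval the loss at 104 per arm is about 4 points (67% to 63%), and the better methods miss 70% there too.
- **That sparse data leave no margin verdict at all.** The SAP says Fisher's tests will be performed and reported, not that they replace the Yates interval. For the Wilcoxon test, the same section says outright that it replaces the t-test. If Fisher is an addition, the Yates limit still gives a verdict, as with −5.8 points for 83/86 in both arms. An exact interval for the risk difference may also have been meant.
- **That the same fault affects other antigens.** SAP 4.1.2 dichotomises by Table 3 to report protection and states no margin for those endpoints.

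It is also fair that Yates errs on the safe side: it does not inflate false claims of non-inferiority. And the SAP disclaims power on this endpoint. What remains is that Fisher's test cannot address the margin, that its role and interval are undefined, and that the correction buys conservatism a valid interval does not need.

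**Conclusion.** The point holds in limited form. Fisher's exact test gives no answer on the -10 point margin. The SAP leaves open what its interval estimates, when it applies and whether it displaces the risk-difference interval, so the rule could be settled after the data are seen. The Yates interval costs about 4 points of power against Miettinen-Nurminen in the final design (66.2% v 70.6%) and runs at 3.5% type I error against a nominal 5%. The power statement in 2.2 is out of date for the design in force rather than shown to be wrong.

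These figures rest on 91% protection in both arms and an even 86/86 split. The 94% trigger for Fisher rests on the assumed rule of five. The analysis supports the GMC primary endpoint, whose test is unaffected.

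**What to change.** - In 4.1.1, base the -10 point verdict on one risk-difference interval without continuity correction: the one-sided 95% Miettinen-Nurminen score limit. For sparse tables, name an exact unconditional interval for the risk difference and state the expected-count threshold that triggers it.
- Keep Fisher's exact test, if wanted, as a descriptive test of equality, and say that it plays no part in the margin decision.
- In 2.2, restate seroprotection power for the final design, with n, alpha and method: about 71% (Miettinen-Nurminen, 86 per arm, one-sided 5%), or about 66% if Yates is kept.
- Make no change to 4.1.2 on this account.

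The cost is a few sentences of SAP text and standard software; no new data are needed. The downside is a rule slightly less conservative than Yates, with type I error still about the nominal 5%. If the 5-month analysis has already been run, record the change as a deviation under 4.3 and show the Yates result beside it.
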